**6.3.4 Software**

All statistical analyses will be performed using Statistical Analysis Software (SAS®) Version 9.3 or higher.

The PK analysis will be performed using WinNonlin Professional Software Version 6.3 or higher.

**6.3.5 Missing Data**

There will be no imputation of missing data.

**6.3.6 Interim Analysis**

No formal interim analysis is planned. Baseline data may be reported when available.

**6.3.7 Protocol Deviations**

PAREXEL Biostatistics and Sponsor will determine the deviations to be included in the CSR and the impact classes of deviations will have on the final datasets. Both PAREXEL Biostatistics and Sponsor have input into, and review, the Protocol Deviation Specifications and Protocol Deviation Report throughout study life cycle and review/reconciliation of deviations.

All protocol deviations will be recorded by the Investigator.

A first determination of whether protocol deviations should be considered major or minor will be performed internally at PAREXEL (e.g. physician, Data Manager, Biostatistician, Pharmacokinetic (PK) Scientist/Analyst and Medical Writer), based upon the Protocol Deviation Specifications, Version 2.0, dated 22-Jan-2019 or later if an update is made between DRM and finalization of this SAP. During the data review meeting (DRM) and before database lock, protocol deviations and their classification as major or minor will be discussed with the responsible study team at the Sponsor

Time window deviations will be listed, including procedure, actual time, scheduled time and deviation (if feasible to calculate). An additional listing will show all other protocol deviations, including description, date, category, classification (major/minor) and consequent exclusions from specific analyses (if any).

**PAREXEL International**  
**Statistical Analysis Plan**

### **6.3.8 Disposition**

Disposition data will be displayed using the ITIFAS.

The patient disposition will be summarized as follows:

- Number of patients dosed.
- Number of patients who completed each period.
- Number of patients who withdrew within each period, including reason of withdrawal.
- Number of patients who were discontinued due to not achieving ITI success in the ITI period by unfulfilled success criteria (see Section 6.1.5.3).
- Number of patients who completed the end of treatment visit.
- Number of patients who were discontinued due to relapse in the tapering period.
- Number of patients assigned to each analysis population.

Date of informed consent, withdrawals and the assignment of patients to the different analysis populations will also all be listed.

### **6.3.9 Demographic Data**

The following demographic data will be listed and summarized using the ITIFAS: age, geographic location, weight, BMI and height at screening, gender, race and ethnic origin. In addition, height at the End of Treatment visit will be included in the listing.

### **6.3.10 Medical History**

The ITIFAS will be used for all listings and summary tables which are related to medical history. For each of the following subsections, the data will be listed, including the variables described in Section 6.1.3.

#### **6.3.10.1 Haemophilia History Including Treatments**

The following summaries will be presented for the history of haemophilia:

- Summary table, including counts and frequencies for severity of haemophilia, as well as family history and descriptive statistics for age at diagnosis

**PAREXEL International**  
**Statistical Analysis Plan**

- Summary table, including:
  - Descriptive statistics for total consumption (IU and IU/kg) of FVIII in the last 12 months – overall and stratified by whether taken concomitantly with bypassing agents
  - Absolute and relative frequencies for different FVIII products
  - Absolute and relative frequencies for the use of by-passing agents in the last 12 months
  - Descriptive statistics for the total consumption of bypassing agents – overall and stratified by whether taken concomitantly with FVIII products
- Blood groups and genotyping, including counts and frequencies of different FVIII mutation types, mechanism and HLA allotypes. The FVIII mutation and HLA allotyping summary will not consider whether the data is collected from existing medical records or from samples analysed at central laboratory.

For summaries of consumption, a subject who did not take that specific product will be counted as having a consumption of zero.

#### **6.3.10.2 Inhibitor History**

The following summary will be presented for the history of inhibitor development:

- Absolute and relative frequencies for:
  - Last product used prior to inhibitor development
  - Last dosing frequency prior to inhibitor development
- Descriptive statistics for:
  - Exposure days at first inhibitor development
  - Last weekly dose prior to inhibitor development
  - Historical peak titer levels
  - Age at inhibitor development

**PAREXEL International**  
**Statistical Analysis Plan**

- Time between first inhibitor development and start of rFVIIIFc treatment in this study, estimated as the difference between age at start of treatment and age at first inhibitor development

#### **6.3.10.3 ITI History**

The following ITI history summary will be presented for all previous ITI attempts:

- Absolute and relative frequencies for:
  - Number of ITI attempts
  - ITI treatments products (FVIII and Other) used in at least one ITI attempt for the patient. In addition, the absolute frequency per product counted by ITI attempt instead of per subject will be given
  - Reason for ITI treatment failures (per subject and for absolute frequencies also per attempt)
- Descriptive statistics for:
  - Number of ITI attempts, duration, dosing/factor consumption, outcomes (bleeds), inhibitor titer before start of ITI, duration of ITI attempts, attempts with and without concomitant use of bypassing agents, peak inhibitor during treatment and inhibitor at end of treatment (only the last treatment per patient will be considered)

All treatment attempts will be listed. This listing will also display the number of recorded historical bleeds that started during the treatment attempt and whether bypassing agents use was also recorded for the time span of the attempt (any overlap counts).

#### **6.3.10.4 Bleeding History**

The following summary will be presented for history of bleeding using the ITIFAS:

- Descriptive statistics calculated for the total number of bleeding episodes per patient and counts and frequencies of bleeding during the last 12 months per location, cause and treatment

**PAREXEL International**  
**Statistical Analysis Plan**

**6.3.10.5 HIV and Hepatitis Status**

The patient HIV and Hepatitis status will be listed using the ITIFAS, including the variables listed in Section 6.1.3.8.

**6.3.10.6 Allergy History**

The history of allergy to FVIII products and other products like bypassing agents will be summarized, showing:

- Counts and frequencies per product type and type of reaction

Other allergies will be included as general medical history.

**6.3.10.7 Other Medical History**

Medical and surgical history will only be listed, including allergies not covered by Section 6.3.10.6.

**6.3.11 Concomitant Medication**

All concomitant medication will be listed including medical coding and summarized using Anatomical Therapeutic Chemical (ATC) categories, levels 2 and 4. For the purpose of both listing and summary the medication given to the breastfeeding mother will be considered concomitant medication. Whether the medication was given to the patient or the breastfeeding mother will be displayed in the listing.

The ITIFAS will be used for these outputs.

**6.3.12 Analysis Related to the Primary Objective**

**6.3.12.1 ITI Treatment Outcome**

The number and proportion of patients achieving each of the ITI success criteria, overall ITI success, partial success and treatment failure will be calculated and displayed in a summary table.

Partial success will also be further subdivided, depending on whether the second or the third criterion for success was achieved.

Treatment Failure will also be further subdivided by primary reason of failure, using the treatment failure criteria defined in Section 6.1.5.3.

## PAREXEL International

### Statistical Analysis Plan

Prognostic factors for ITI success will be summarized stratified by ITI outcome. Prognostic factors to consider include; historical peak inhibitor titer, pre-ITI inhibitor titer, factor VIII genotype, peak inhibitor titer on ITI, number of previous ITI attempts, time between inhibitor development and start of ITI. In this summary, patients will be included according the best ITI outcome they achieve (partial success is not also counted as failure and complete success is not also counted as partial success). The following categorical variables will be derived for this summary:

- Historical Peak Inhibitor Titer <200 BU (yes/no)
- Pre-ITI Inhibitor Titer <10 BU (yes/no)
- >5 Years between Diagnosis of Inhibitor and Start of ITI (yes/no)

The ITIFAS analysis set will be used for this analysis.

A figure will be presented showing the number and percentages of patients by ITI outcome versus time (up to Week 60, patients will be counted for each time point after their ITI outcome has been determined, regardless of discontinuation or relapse).

In addition, a treatment outcome listing will be produced, displaying for each patient:

- Outcome (ITI success, partial success, failure or not determinable [if withdrawal due to other reasons prior to 60 weeks])
- Study day each of the success criteria was met (blank if not met)
- Relapse (no or relapse criteria met)
- Days after ITI success to relapse

#### **6.3.12.2 FVIII:C Levels**

For the FVIII:C the following listings will be produced:

- All local laboratory FVIII:C measurements, including period, visit, assay used, date, nominal and actual time, purpose of sample and result (absolute value for all samples).
- All determinations of incremental recoveries, based on results from local laboratory including period, visit, date, observed and expected IR (incl. units), and ratio of observed to expected IR (as percentage) (see Section 6.1.5.2.2 for derivation). Determinations that indicate either confirmed IR  $\geq 66\%$  of the expected IR, ITI success (complete or partial) or relapse will be flagged for the recorded observed/expected percentage. The listing will also contain whether the investigator considered the IR to be  $\geq 66\%$  and flags where this contradicts the derived ratio.

## PAREXEL International

### Statistical Analysis Plan

- All determinations of terminal half-life, based on results from local laboratory, including period, visit, date and the calculated terminal half-life. Determinations that indicate either confirmed half-life  $\geq 7$  hours, ITI success (complete or partial) or relapse will be flagged.
- If the measured FVIII:C is below the LLOQ, it will be indicated as BLQ in any listing.

The ITIFAS analysis set will be used for the listings. A figure will show the FVIII:C versus Study Day, with different symbols to indicate assay type and different colours to indicate time point relative to dose.

#### **6.3.12.3 Central and Local Laboratory Comparison**

As an exploratory analysis, the following summary tables will be presented using the ITIFAS:

- 2x2 table of local vs central laboratory on observed IR  $> 66\%$  of the expected IR
- 2x2 table of local vs central laboratory on terminal half-life ( $t_{1/2z}$ )  $\geq 7$ h
- 2x2 table of local vs central laboratory on inhibitor titer  $< 0.6$  BU/mL

Both the local and central laboratory results will also be listed; IR and ( $t_{1/2z}$ ) will be listed together. A separate listing will be shown for the inhibitor titer comparison.

For both FVIII:C and titer levels scatter plots will be presented by period and visit, showing the local laboratory results on the x-axis and the central laboratory results on the y-axis. A line with intercept zero and slope one will be added to indicate a perfect fit. Any BLQ values will be shown at zero.

#### **6.3.12.4 Titer Levels**

Absolute values, change from baseline and percent change of baseline of the inhibitor titers will be listed, including all the variables in the CRF (see Section 6.1.5.1). In addition, period and visit will be included and used for chronologically sorting of the listing. The measurements will be flagged, if they indicate one of the following:

- Confirmed negative titer
- Relapse (criteria 1 in Section 6.1.5.4)

The titers (absolute values, change from baseline and percent change from baseline) will also be summarized descriptively by time-based visit for the ITI period. Values below the lower limit of the quantification (LLOQ) will be displayed as BLQ (below the lower limit of quantification) in listings and

**PAREXEL International**  
**Statistical Analysis Plan**

treated as zero for the calculation of change from baseline, percent change from baseline and any descriptive statistics.

In addition, the following figures will be produced for the ITI period only:

- Titers versus actual study week by patient in linear scale and semi-logarithmic scale
- Mean titers ( $\pm$  standard deviation) versus nominal time in linear scale and semi-logarithmic scale

The standard deviation will be shown in linear scale only.

As patients leave the ITI period after a different amount of time, the mean figures will be produced for a full 60 weeks after study start, and values for patients that are no longer in the ITI-period due to ITI success will be replaced with zero, including those cases where the subjects relapse within the tapering/follow-up period. The same will be done for any values that are below the LLOQ.

Since the frequency of visits depend on the titer levels, time-based visit (see Section 6.3.1.1) will be used for the mean plot.

The baseline visit measurement will be used to calculate changes from baseline.

The ITIFAS analysis set will be used for the listings, the summary tables will be produced using the analysis set that corresponds the period being displayed.

### **6.3.13 Analysis Related to the Secondary Objectives**

#### **6.3.13.1 Time to ITI Success**

Time to ITI success in weeks will be analysed with descriptive summary statistics. The same will be done for patients achieving confirmed negative titer, confirmed incremental recovery  $> 66\%$  of the expected IR and the time until terminal half-life criteria is met respectively. For the descriptive analysis, the time for a patient who either never reaches the criteria or for whom the criteria are never assessed due to not fulfilling the required condition will be considered to be missing.

Time [week] to ITI success will also be analysed descriptively using Kaplan-Meier estimates including median, 25th and 75th quantile. It is considered likely that it will not be possible to provide estimates for the median and the quantiles, due to the success rate not being high enough and the proportion of censored data being too high. Each subsequent week then starts on the seventh day after the first day of the previous week.

**PAREXEL International**  
**Statistical Analysis Plan**

Patients who do not achieve ITI success will be treated as follows:

- Patients who discontinued because there was no downward trend of 20% in titers will be considered censored at the time of treatment failure.
- Other patients are considered to be censored at the last observed time. This includes patients who withdrew due to safety concerns or who did not achieve the criteria for ITI success within 60 weeks of starting ITI with rFVIIIFc.

A Kaplan-Meier plot of the cumulative probability of success function will be generated by using the PROC LIFETEST in SAS software.

The following code (or similar code) will be used:

```
PROC LIFETEST DATA = iti_success PLOTS = SURVIVAL;
  TIME success_time * censored (1);
RUN;
```

The same analysis will also be done for the following:

- Time to confirmed negative titer
- Time to confirmed incremental recovery >66% of the expected IR

The ITIFAS analysis set will be used for this analysis. Week for the purpose of this analysis will be defined as follows: the study day/7, rounded up.

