### 7.1.2 ITI period

The first dose of rFVIIIFc will be administered at the baseline visit and the ITI treatment will continue until ITI success or failure is declared, or for a maximum of 60 weeks. The ITI regimen

consists of daily administration of rFVIIIFc (200 IU/kg per day), which may be given as once daily injection or divided in two injections per day at the discretion of the investigator.

Visits will occur 2 and 4 weeks after the baseline visit and then every 4th week. For patients who achieves an IR >66% of the expected IR for each specific patient as per investigator judgment, the visit frequency will be changed to every other week.

During the ITI period patients will undergo procedures and assessments as per the schedule of events (Table 1). Samples for inhibitor testing and assessment of FVIII:C levels will be analyzed at the local laboratory as well as centrally. The results from the local laboratory will constitute the primary data of the study to be used for statistical analysis.

At each visit the inhibitor titer will be assessed. If, after the initial 3 months, a downward trend of at least 20% in the inhibitor titer in any 6-month period is not seen, the patients should be regarded as a treatment failure and complete the end of treatment visit as soon as possible.

The assessment of ITI outcome is illustrated in Figure 2. Once a patient has demonstrated negative inhibitor (<0.6 BU/mL) at two consecutive visits, evaluation of IR will be performed at the next visit. When an IR >66% of the expected IR has been obtained at 2 consecutive visits, pharmacokinetic assessments to determine half-life will be performed at the subsequent visits until a half-life of  $\geq 7$  hours is attained. Patients are required to have at least a 24-hour washout prior to the half-life assessment.

An unscheduled visit after the 60-week period may be scheduled to allow the patient to get a confirmatory test, as long as the first test occurred during the 60-week period. If the second test confirms the results of the first test, the date of ITI outcome is the date of the first value, which occurred during the 60-week period. Fluctuations in inhibitor levels is common and variability in inhibitor titer is expected. Patients will be evaluated on a case-by-case basis.

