#### **7.1.4 Follow-up period**

After completion of the tapering period, patients will enter the follow-up period. During the follow-up period patients will be treated prophylactically for up to 32 weeks with dose and frequency prescribed by the investigator, and according to the label and clinical response of the patient. If the tapering period has been prolonged, the follow-up period should be shortened accordingly but should not be less than 24 weeks.

During the follow-up period patients will visit the clinic every 12 weeks and undergo procedures and assessments as per the schedule of events (Table 2). At each visit, samples for inhibitor titer and IR assessments will be drawn to monitor for relapse. A patient with confirmed relapse criteria will complete the end of treatment visit.

In order to avoid bleeds and a relapse of the inhibitor titer, FVIII:C levels should be kept  $\geq 1$  IU/dL. Bleeding episodes during the follow-up period should be treated with rFVIIIFc, with doses according to investigator judgment and local practice. In specific situations, e.g. if bleeding is unresponsive to treatment with rFVIIIFc, treatment with bypassing agents may be considered as judged by the investigator. Such use is to be notified to the medical monitor and the rational documented in the medical records. Patients with bleedings during the follow-up period is to be tested for recurrence of inhibitors.

At the end of treatment visit, pharmacokinetic assessments to determine IR and half-life, if deemed measurable based on pre-dose FVIII:C, will be performed. Patients are required to have at least a 24-hour washout period prior to the half-life assessment.

Throughout the follow-up period rFVIIIFc administration and any bleeding episodes will be registered by the patient and/or his caregiver in a study-specific diary. The diary data will be reviewed by the investigator on an ongoing basis and discussed with the patient at each visit.

After the patient has completed the end of treatment visit, they should be treated and followed-up according to investigator judgment and local practice. No further investigational medicinal product will be provided.

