### **9.3.4 Analysis related to secondary objective**

#### **9.3.4.1 Time to ITI success**

Time to ITI success will be analyzed descriptively using Kaplan-Meier estimates including median, 25th and 75th quartile. A Kaplan-Meier plot will be generated. Patients not achieving ITI success during the up to 60 weeks ITI period will be censored at the last observed time for this analysis. The ITIFAS analysis set will be used for this analysis.

Time to ITI success will also be summarized descriptively for the patients achieving ITI success.

Time to confirmed negative titer will be analyzed in the similar way.

Time to confirmed Incremental recovery >66% of the expected IR will be analyzed similarly as well on the subset of patients who reached confirmed negative titer.

For the subset of patients who were classified as partial success at the end of the ITI period, the time to fulfillment of the criteria for partial success will also be analyzed descriptively.

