**Treatment Failure**

Treatment failure is defined as fulfilling one of the following three criteria:

1. No downward trend of at least 20% in the inhibitor titers in the six (6) months after the initial three (3) months of ITI treatment
2. Presence of a sustained positive inhibitor ( $\geq 0.6$  BU/mL) after 60 weeks of ITI
3. Negative inhibitor titer without either achieving  $IR > 66\%$  of expected IR or Terminal half-life  $t_{1/2z} \geq 7$  hours after 60 weeks of ITI

For each patient who fulfils at least one of the three criteria, the one with the lowest criterion number will be considered to be the primary reason for failure.

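### Patients declared early treatment failures are censored in the Kaplan-Meier analysis of time to ITI success, so from about week 36 the curve can overstate the probability of success

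*SAP*

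**What the plan says.** SAP 6.3.13.1 (Time to ITI Success) analyses time to success by Kaplan-Meier in the ITIFAS, that is, all patients who received at least one dose. For early no-trend failures the rule is: "Patients who discontinued because there was no downward trend of 20% in titers will be considered censored at the time of treatment failure". All other non-successes, including withdrawals, are censored at their last observed time. The SAS statement has a single censoring code, "TIME success_time * censored (1", so declared failures and withdrawals enter in the same way. The output is described thus: "A Kaplan-Meier plot of the cumulative probability of success function will be generated". The same analysis is then applied to time to confirmed negative titer and time to confirmed IR above 66% of expected.

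Protocol 9.3.4.1 has the same approach in general form: "Patients not achieving ITI success during the up to 60 weeks ITI period will be censored at the last observed time for this analysis".

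The failure criterion behind the first rule is in SAP 6.1.5.3: "No downward trend of at least 20% in the inhibitor titers in the six (6) months after the initial three (3) months". Under Protocol 7.1.2, "the patients should be regarded as a treatment failure and complete the end of treatment visit as soon as possible". On what follows that visit, the Protocol says "No further investigational medicinal product will be provided". This sentence stands in 7.1.4 and also, as a general statement covering all patients, in 7.4.2.

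**The concern.** Kaplan-Meier censoring is suitable for a patient whose later outcome is unknown and who could still have the event at the rate of those still under observation. A no-trend failure is different. His ITI outcome is settled, he has stopped study ITI, and he was removed because his titer did not fall. A negative titer is the first success criterion, so the censoring is informative by construction.

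At stake is the meaning of the first-listed secondary endpoint. The objective is time to tolerization within 60 weeks in the patients treated, and the plot is presented as their cumulative probability of success. If early failures are censored, the curve estimates success in a hypothetical setting without early failure. It may then show a higher week-60 percentage than the primary table. It may also print a median that is too early, or a median when fewer than half of the patients succeed.

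**Working it through.** **When the problem can start.** The Protocol (7.1) and SAP (section 2) give a minimum participation of 4 + 36 + 2 = 42 weeks, which reproduces. The 36 weeks of ITI match 3 + 6 months at 4 weeks each; nine calendar months are 9 × 30.4375 / 7 = 39.1 weeks. The horizon is 60 weeks. Failure criteria 2 and 3 apply only after 60 weeks, so only criterion 1 matters, and only between about week 36 and week 60. Before the first early failure, censoring these patients changes nothing.

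**Direction.** At a success time with *d* successes among *r* at risk, Kaplan-Meier adds S_KM × d/r. Aalen-Johansen adds S_all × d/r, where S_all is the probability of neither success nor early failure so far. Since S_all ≤ S_KM, Kaplan-Meier is never the lower of the two. It is strictly higher after any success that follows an early failure.

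**Size.** Neither document gives an expected number of successes or failures, so the following inputs are assumptions, apart from N = 20 and the 60-week limit. Let E be successes before the early failures, F early failures, L later successes, W withdrawals at week 40, and R = 20 − E − F. All others are followed to week 60.

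Without withdrawals:
- Kaplan-Meier at week 60 = 1 − (1 − E/20) × (R − L)/R
- Aalen-Johansen at week 60 = (E + L)/20

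Example with E = 4, L = 3, F = 8 at week 39: R = 8, so Kaplan-Meier = 1 − 0.80 × 5/8 = 50.0%; Aalen-Johansen = 7/20 = 35.0%.

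Kaplan-Meier at week 60, with 7 successes in total in every row (Aalen-Johansen 35.0% throughout):

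| Scenario | F=4 | F=6 | F=8 | F=10 |
|---|---|---|---|---|
| Failures week 39, no later success | 35.0% | 35.0% | 35.0% | 35.0% |
| Failures week 39, one later (week 44) | 37.0% | 38.8% | 41.7% | 47.5% |
| Failures week 39, three later (weeks 44, 50, 56) | 40.0% | 44.0% | 50.0% | 60.0% |
| Failures week 48, same success times as previous row | 38.6% | 41.7% | 46.4% | 55.0% |

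With failures at week 39, only F = 10 with three later successes clearly prints a median (week 56: 0.80 × 3/6 = 0.40 still without success). F = 8 sits exactly at 50%, so a median there depends on the convention used.

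With W = 3, failures at week 39, E = 4 and L = 3:
- Kaplan-Meier = 1 − 0.80 × (R − 6)/(R − 3)
- Aalen-Johansen = 0.20 + (R/20) × 3/(R − 3)

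| | F=4 | F=6 | F=8 |
|---|---|---|---|
| Kaplan-Meier | 46.7% | 54.3% | 68.0% |
| Aalen-Johansen | 40.0% | 41.4% | 44.0% |

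Here Kaplan-Meier prints a median of week 56 (F = 6) or week 50 (F = 8). The Aalen-Johansen median is not reached in either case.

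**A low success rate.** With E = 1, L = 1 (week 44) and failures at week 39, Kaplan-Meier is 1 − 0.95 × 14/15 = 11.3% for F = 4 and 1 − 0.95 × 10/11 = 13.6% for F = 8, against 2/20 = 10.0%.

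**The case against.** The strongest case is that the practical effect may be small.

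- **Timing.** Protocol 5.1.2 reports tolerance with this product at 17 weeks, 18 weeks and 17 months, normal recovery at 3, 14 and 65 weeks, and a normal half-life at 27 weeks. None falls between weeks 36 and 60, and without a success in that window the bias is zero. This supports caution about size. But the cases are few and mixed, individual times to negative titer are not given, and that series ran to 67.6 weeks, so late events are not excluded.
- **Success rate.** The assumed 35% has no support in the documents. In the rescue series of 12 described there, one patient is reported to have reached a normal half-life. The SAP itself expects quantiles not to be estimable, "due to the success rate not being high enough and the proportion of censored data being too high". At 10% success the excess is 1 to 4 points with no spurious median. That stands as a limit on size, but the bias remains upward, and the SAP's remark does not correct the curve.
- **Extreme scenarios.** The 60% and 68% results leave only six and five patients at risk after the early failures and withdrawals. They show what is possible, not what is likely.
- **Other outputs.** SAP 6.3.12.1 already plans a figure of ITI outcome against time that keeps determined outcomes in the count. Without withdrawals its success line equals the cumulative incidence. This helps the reader, but it does not replace the planned Kaplan-Meier tables, plots and quantiles, which could then disagree with it without explanation.
- **IR analysis.** Protocol 9.3.4.1 restricts time to confirmed IR to patients with a confirmed negative titer, which would exclude most no-trend failures. The SAP, however, uses the ITIFAS, where the problem applies.
- **Remedy.** A footnote might be enough for a descriptive secondary curve. It would warn the reader but leave the quantiles uncorrected.

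**Conclusion.** The concern holds. Early no-trend failure ends the possibility of success in the study, yet it is censored together with withdrawals, and no cumulative-incidence estimate is planned. The error can only go upward, and only if at least one success follows at least one early failure. Under the assumptions shown, the excess at week 60 runs from zero through 1 to 4 points (2 successes in 20) to 25 points (7 successes, three of them late, 10 early failures, no withdrawals). The documents cannot narrow this range.

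The consequence is limited. The study is descriptive, without tests or confidence intervals. The primary proportions, the outcome-versus-time figure and the curves before about week 36 are sound. What is affected is how the secondary time-to-event curves and their quantiles are read. Because the correction is simple, it should be made.

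**What to change.** In SAP 6.3.13.1, replace the single censoring indicator with a three-level status: event; early treatment failure under the no-trend criterion, as competing event; censored. Apply it to time to ITI success, time to confirmed negative titer and time to confirmed IR above 66%. Report the Aalen-Johansen cumulative incidence and take the median and quartiles from it. Keep withdrawals, and patients without success at 60 weeks, censored at their last observed time. Align Protocol 9.3.4.1, and settle there and in the SAP which population the IR analysis uses.

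Moving the failures' censoring time to week 60 is not an equivalent shortcut. In the scenario with three withdrawals it gives 1 − 0.80 × 10/13 = 38.5% whatever F is, against 40.0%, 41.4% and 44.0%.

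If the Kaplan-Meier plot is kept, state beneath it that early failures are censored and that the curve is not the proportion of patients who succeed.

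The cost is a wording change, one recoded variable and a standard procedure for three endpoints, with no new data. The reported curve can only stay the same or become less favourable.
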